coordinator's phone number in case they require additional information or want to discuss aspects of the study, as well as to indicate interest in the study. For those who did not respond to the letter within two weeks of mailing, the study coordinator will contact them over the phone to explain the study and determine interest in participating. For all those interested in participating, the study coordinator will arrange a date and time to meet in the clinic. Details of the study and the consent form will be reviewed in-person at this time to ensure that patients are fully informed about all aspects of the study and are freely providing their consent to participate.

To perform a sample size calculation, the primary outcome measure SF-36 was used. Assuming a moderate effect size on the general health dimension of the SF-36 of 10.5 points (39), a score of 57 +/- 21 for the control group (40), 80% power, and alpha=0.05 (two-sided), the sample size per group was calculated to be 63 (<http://clincalc.com/Stats/SampleSize.aspx>). Assuming 15% of patients will be lost to follow-up (including mortality) (36, 37), the sample size per group is 73. Hence 146 patients will be enrolled during the trial and randomized 1:1 into control and telemonitoring groups.

To perform the randomization, the online computer generated randomization tool, Research Randomizer, will be used ([www.randomizer.org](http://www.randomizer.org)). The study coordinator performing the recruitment will be blinded until the patient has consented to participate. The participants will be blocked randomized (blocks of 4) and stratified into groups according to their primary condition (HF, COPD, hypertension, insulin-requiring diabetes, and CKD). The HF group will further be stratified based on NYHA classification (NYHA class 2-3, NYHA class 4), and the hypertensive patients will be stratified to those with and those without diabetes.

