## **Outcome Measures:**

The primary outcome will be health status as measured with SF-36 because this metric will be relevant to all chronic conditions under investigation. A secondary

outcome measure will be the cost (from the health system and patient perspectives). The cost of healthcare will include hospitalizations, emergency department (ED) visits, clinic visits, delay of hemodialysis commencement, medications, and telemonitoring program, as relevant to the different chronic illnesses and will include disease-specific sub-analyses.

Other secondary outcome measures will include combined hospitalization for any reason or death from any cause within 6-months after enrolment, hospitalization, mortality, days in hospital, number of emergency department (ED) and clinic visits, and medications. Secondary outcome measures will also include general quality of life as measure by the EuroQol 5D-RL, anxiety and depression as measure with the Hospital Anxiety and Depression Scale (41) and patients' self-efficacy to self-manage their disease as measured with the Self-Efficacy for Managing Chronic Disease Scale (42) (Appendix 3).

Disease specific outcome measures will include:

- HF
  - left ventricular ejection fraction (LVEF)
  - brain natriuretic peptide (BNP)
  - self-care as measured by the Self-Care of Heart Failure Index (43) (Appendix 4)
  - Heart-failure specific quality of life as measured by Minnesota Living with Heart Failure Questionnaire (44) (Appendix 4)
  - Shortness of breath as measure using a visual analogue scale (VAS) for dyspnea (Appendix 4)
  - Blood work: creatinine, sodium, potassium, hemoglobin, urate
  - Prognostic score as determined by the Seattle Health Failure Model (requires: age, gender, NYHA class, weight, ejection fraction, systolic BP, medication list (including diuretics), lab results (hemoglobin, lymphocytes, uric acid, total cholesterol, sodium) and QRS interval)
- COPD
  - forced expiratory volume in one second (FEV1)
  - symptoms score from the telemonitoring system
  - COPD Assessment Test (CAT) score (45) (Appendix 5)
  - COPD-specific knowledge after 6-months of application usage, as measured by the Bristol COPD Knowledge Questionnaire (BCKQ)(46) (Appendix 5)
  - patient self-efficacy at 6 months as measured by the COPD Self-Efficacy Scale (CSES)(47) (Appendix 5)
  - COPD severity as measured by the BODE Index(48) at 6 months (Appendix 5)

- CKD
  - estimated glomerular filtration rate (eGFR)

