  - symptoms score from the telemonitoring system
  - blood pressure as measured by an automatic blood pressure monitor
- Hypertension
  - blood pressure as measured by an automatic blood pressure monitor
  - average 7-day blood pressure
- Diabetes
  - HgbA1c

**Data Acquisition:** Number of hospitalizations, days in hospital, number of ED and clinic visits, and medications will be determined through the hospital EMR and a manual chart review of all participants' clinical records. Combined hospitalization will be verified by patient participants through self-report with the help of a questionnaire. The cost of the intervention will be tracked, including for equipment costs and human resources for clinical support, technical support, and program management. Standard cost values for a day in-hospital, ED visit, etc. will be used to estimate net cost savings or expenditures. Values for pre- and post-trial health outcome measures (eg, blood test results) will be obtained through hospital clinical records or through the *Medly* database for symptoms. Pre- and follow up questionnaires (baseline, 1-month, and 6-months), will be administered to both control and intervention groups that contain the validated survey tools listed above. Participants will be able to complete the questionnaires at the clinic or complete it at home. Participants that chose to complete the questionnaire at home will be given a pre-paid self-addressed envelope to mail the questionnaire back to the study team. The 1-month questionnaire will be given to participants upon enrolment with instructions to complete the questionnaire one month after starting the trial and to mail it back to the study team using the pre-paid envelope. The study coordinator will call each participant at the 1-month period to remind participants to complete the questionnaire. In addition to the baseline and follow up questionnaires that are applicable to all patient participants (Appendix 3), patients with HF and/or COPD will also receive the validated survey tools listed above (Appendix 4 and 5). Average 7-day blood pressure will also be recorded from patients with a primary diagnosis of hypertension during their first week in the study (baseline) and their last week in the study (6-months). To do this, patients will be provided with a digital blood pressure monitor which they will use to take blood pressure 4 times per day (2 times in the morning and 2 times in the evening) over each 7-day period. Patients will return the blood pressure monitor to the study team who will download the

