**Data Analysis:** Post-trial data and change scores will be compared between the control and intervention groups using independent Student t tests and Mann-Whitney tests (for normally and not normally distributed data, respectively). Paired Student t tests and Wilcoxon signed rank tests will be performed to compare baseline and post-study data within the control and telemonitoring groups. The statistical analyses will be performed using the statistical software application SPSS (IBM Corporation, USA). The cost evaluation will be performed by comparing any savings through reductions in hospitalization, emergency and clinic visits, through the use of the intervention. This will further include amortizing the equipment costs and factoring in additional clinical, technical, and management resources. An analysis of indirect costs will also be performed, such as days absent from work. Interview data will be analyzed using a conventional content analysis approach (49). Two researchers will analyze the transcripts independently and code the transcripts with the software program NVivo (QSR International, Doncaster, Victoria, Australia).

The Principle Investigator will keep all study data in a secure and confidential location for 10 years after the completion of the study and then they will destroyed by shredding of paper or erasing of digital information. All participants will be assigned a unique identifier, which will replace any identifiable information contained in the research data. A list linking the study number with the participants' name will be kept by the Principle Investigator in a secure place in a locked cabinet.

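### No pre-enrolment look-back is specified for hospital use or cost and the planned comparisons are unadjusted, so precision on these secondary outcomes is given up although the planned chart review could probably supply the baseline

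*Combined protocol and SAP*

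**What the plan says.** The Central Research Question under Objectives includes cost and health service utilization. Outcome Measures lists admissions, days in hospital, ED visits, clinic visits and cost as secondary outcomes. On their source, the Data Acquisition paragraph says "Number of hospitalizations, days in hospital, number of ED and clinic visits, and medications will be determined through the hospital EMR", with charts reviewed by hand as well. No time window is attached to that review. The one dated outcome in this group is combined hospitalization or death, counted "within 6-months after enrolment".

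The baseline data that the same paragraph does describe are health outcome measures (blood tests are the example), the questionnaires and the 7-day blood pressure. Hospital use and cost are not named among them.

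The Data Analysis paragraph says "Post-trial data and change scores will be compared between the control and intervention groups", using t tests or Mann-Whitney tests according to distribution, with paired tests within each arm. It does not say which outcomes get a change score. No covariate is planned for any outcome, and the tests do not use the randomization strata. The cost evaluation refers to reductions in use without saying whether the reference is the control arm or an earlier period.

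**The concern.** A patient's earlier hospital use will usually carry some information about later use. If it is neither defined nor used, the predictable part of the variation between patients stays in the error term, and any chance difference between arms in prior use passes in part into the estimate.

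Stratification covers only some of this. Patient Recruitment stratifies by primary condition, by NYHA class within heart failure and by diabetes within hypertension. Eligibility does not require a recent admission, so patients with heavy and with no recent use can share a stratum.

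The gap exists on either reading of Data Analysis. If hospital use gets no change score, prior use is ignored. If it does get one, the baseline period is undefined and could be chosen late. The trial is sized only for SF-36, so these outcomes have no planned power and precision is worth having.

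**Working it through.** **The plan's own figure.** Inputs from Patient Recruitment: "Assuming a moderate effect size on the general health dimension of the SF-36 of 10.5 points", "a score of 57 +/- 21 for the control group", and "80% power, and alpha=0.05 (two-sided), the sample size per group was calculated to be 63".

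- n per arm = 2 × (1.960 + 0.842)² × 21² / 10.5² = 62.8, so 63. This reproduces.
- 63 × 1.15 = 72.45, so 73 per arm and 146 in total, as stated. Dividing by 0.85 instead gives 74.1, a small difference with no bearing here.

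These figures concern SF-36 only. The documents give no event rate, variance or pre/post correlation for hospital use or cost, so everything below rests on assumptions.

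**Gain from adjustment.** Let r be the correlation between the pre-enrolment and on-trial values. Relative to comparing follow-up values alone, linear adjustment multiplies the variance by 1 − r², which is worth 1/(1 − r²) − 1 more patients. A change score multiplies it by 2(1 − r), assuming equal variance in the two periods.

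| Assumed r | Variance removed by adjustment | Equivalent extra patients | Change-score variance factor |
|---|---|---|---|
| 0.17 (days, low) | 2.9% | 3.0% | 1.66 |
| 0.25 (days, high) | 6.3% | 6.7% | 1.50 |
| 0.26 (counts, low) | 6.8% | 7.3% | 1.48 |
| 0.37 (counts, high) | 13.7% | 15.9% | 1.26 |
| 0.50 | 25% | 33% | 1.00 |

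The count and day ranges come from simulation in which a patient's risk is not fully stable over time. The value r = 0.5 is the top of a stable-risk calculation. For gamma-Poisson counts with mean μ and between-patient variance v, r = μv/(1 + μv). With μ = 0.5 admissions per 6 months, that is 0.5/1.5 = 0.33 at v = 1 and 1/2 = 0.50 at v = 2.

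**Sensitivity to event frequency.** A further simulation used 63 per arm, held each patient's rate constant across both periods, and adjusted for log(1 + prior count).

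- Rare events (mean 0.3 to 0.6 per 6 months, look-back 6 or 12 months): variance ratio 0.68 to 0.99 against follow-up values alone. With a 6-month look-back, change scores gave 0.96 to 1.74.
- Frequent events such as clinic visits (mean 3 per 6 months): variance ratio 0.42 to 0.69. Here r exceeded 0.5 and change scores also beat follow-up values alone, at 0.21 to 0.77 over both look-backs.

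Constant risk is favourable to adjustment, so these are optimistic.

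**Chance imbalance in prior admissions.** With μ = 0.5 and 73 per arm, the SD of the arm difference is √(μ + vμ²) × √(2/73).

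- v = 1: √0.75 × 0.166 = 0.14, or 29% of the mean.
- v = 2: √1.00 × 0.166 = 0.17, or 33% of the mean.

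Only r times this reaches the on-trial estimate: 0.26 × 29% to 0.37 × 33%, about 7 to 12% of the mean at one SD.

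In standardized terms with 63 per arm, the SD of the imbalance is √(2/63) = 0.178. The chance that it exceeds 0.2 SD is about 26%, and its 95% range is ±0.35 SD. The part carried over is ±0.07 SD at r = 0.2 and ±0.14 SD at r = 0.4. All of these imbalance figures ignore stratification, which lowers them to the extent that the strata explain prior use.

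**The case against.** Several stronger readings are tempting, and the documents do not support them.

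- **That the plan uses no baseline for these outcomes.** This would be inferred from silence. The chart review has no stated window in either direction, and Data Analysis mentions change scores and paired baseline tests without naming outcomes. The supportable statement is that no look-back is specified. The dated phrase "within 6-months after enrolment" belongs to the combined hospitalization or death outcome, not to the counts. Medications sit in the same list, but Methods has baseline medication lists entered in the telemonitoring dashboard, so the point does not extend to them.
- **That the comparison is biased.** Follow-up values can be compared between randomized arms without a baseline. Chance imbalance is ordinary sampling error, already reflected in the standard error, so the type I error is not inflated.
- **That a few heavy users dominate the counts.** Data Analysis assigns Mann-Whitney tests to non-normal data, and ranks limit the pull of extreme values. The worry keeps its force for mean cost, but nothing in the documents allows it to be sized.
- **That a quarter of the variance, or a third more patients, is at stake.** That end requires r = 0.5, reached for admissions at μ = 0.5 only with perfectly stable risk and v = 2. Similarly, the imbalance of 29 to 33% of the mean is in prior use and does not pass whole into the estimate.

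These limits stand. They reduce the point to precision on secondary outcomes. They do not remove it, because nothing in the plan fixes a baseline period or uses prior use in the between-arm comparison.

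**Conclusion.** The point holds as a cheap improvement. The plan specifies no pre-enrolment period for admissions, hospital days, ED visits, clinic visits or cost, and its comparisons are unadjusted. The randomized comparison stays valid, and the SF-36 primary outcome and its sample size are unaffected.

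The loss is modest for rare events: about 7 to 14% of the variance for counts and 3 to 6% for days under the assumed correlations. It could be larger for frequent events such as clinic visits if risk is stable. For cost it is not quantified. Every rate, variance and correlation is assumed, and the 1 − r² gain strictly describes linear adjustment; rank tests and count models will differ somewhat. Where r is below 0.5, applying the planned change scores to these outcomes would be less precise than comparing follow-up values alone.

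**What to change.** - **Data Acquisition:** extend the same EMR and chart review to a fixed window before randomization, for example 6 months, for admissions, hospital days, ED visits and clinic visits, extracted the same way in both arms. Derive pre-enrolment cost from these counts with the same standard unit costs.
- **Data Analysis:** for these outcomes, replace change scores with a between-arm model suited to skewed data, for example negative binomial for counts and a gamma or bootstrapped linear model for cost. Adjust for the patient's own pre-enrolment count or cost and for the stratification factors (primary condition, NYHA class within heart failure, diabetes within hypertension). State that the cost reference is the control arm.

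**Cost:** a longer look-back in a review already planned, and confirmation that consent and record access cover the earlier period. No new visits, patients or data source are needed. Two limits should be acknowledged. Care at other hospitals will be captured incompletely, which weakens the correlation. The self-report check planned for combined hospitalization has no counterpart in the look-back period.

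### The plan names no primary SF-36 scale and tests both post-trial and change scores; one baseline- and stratum-adjusted analysis would define the result, protect the 0.05 and gain precision

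*Combined protocol and SAP*

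**What the plan says.** The Outcome Measures section defines the primary endpoint in one sentence: "The primary outcome will be health status as measured with SF-36". It names no scale, summary score or time point.

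The general health dimension appears only in the sample-size paragraph of Patient Recruitment: "Assuming a moderate effect size on the general health dimension of the SF-36 of 10.5 points", with "a score of 57 +/- 21 for the control group" and "80% power, and alpha=0.05 (two-sided), the sample size per group was calculated to be 63". That is one scale and one comparison.

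The between-arm analysis is a single sentence in the Data Analysis paragraph: "Post-trial data and change scores will be compared between the control and intervention groups using independent Student t tests and Mann-Whitney tests". The choice between t and rank tests depends on normality. The paragraph then adds paired tests within each arm. It ranks no contrast, gives no multiplicity rule and includes no covariate.

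Two further facts bear on the remedy. Baseline SF-36 is available in both arms (Data Acquisition: "Pre- and follow up questionnaires (baseline, 1-month, and 6-months), will be administered to both control and intervention groups"). Randomization is stratified ("The participants will be blocked randomized (blocks of 4) and stratified into groups according to their primary condition"), with heart failure split further by NYHA class and hypertension by diabetes. That makes seven strata, none of which enters the analysis.

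**The concern.** Post-trial scores and change scores are both legitimate between-arm contrasts in a randomized trial, but they are different tests on the same data. The plan runs both and does not say which is primary, so a trial in which only one is significant has no defined primary result. The stated 0.05 applies to one pre-specified test on one scale. It is not guaranteed while the contrast and the scale remain open.

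Precision is a separate matter and does not inflate alpha. Baseline SF-36 is used only by subtraction, inside the change score. A covariate model would use the same baseline data more efficiently.

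**Working it through.** **Inputs from the documents.** Difference 10.5, SD 21 (so d = 10.5/21 = 0.5), two-sided alpha 0.05, power 80%, 63 per group before loss and 73 after, 15% loss.

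**Input not in the documents.** The correlation rho between baseline and 6-month score. I take 0.3, 0.5 and 0.7, and up to 0.8 for alpha. Equal variances at the two times are assumed.

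**The plan's own figure.** n per group = 2 × [21 × (1.960 + 0.842)/10.5]² = 62.8, rounded up to 63. This reproduces. The 73 is 63 × 1.15 rounded up. Expected completers are 73 × 0.85 = 62 per arm.

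**Alpha if either contrast could be claimed.** With no effect, the correlation between the post-score and change-score statistics is sqrt((1 − rho)/2), which is 0.592, 0.500 and 0.387 at rho 0.3, 0.5 and 0.7. The bivariate normal gives P(either |z| > 1.96) = 8.8%, 9.1% and 9.4%, and 9.5% at rho 0.8. Each test alone is at 5%.

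**How often exactly one is significant.** With no effect this is 2 × P(either) − 0.10, which gives 7.6%, 8.1% and 8.7%. At the planned effect, the means of the two statistics are 0.5 × sqrt(31) = 2.78 for the post score and 2.78/sqrt(2(1 − rho)) for the change score. One million draws gave 26.9%, 23.0% and 20.6%.

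**Scale.** One contrast tested on two SF-36 scales, either counting, gives 7.8% to 9.3% for an assumed between-scale correlation of 0.8 to 0.4.

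**Power and precision at 62 per arm.** Power is from the noncentral t with standardized effect 0.5 (post), 0.5/sqrt(2(1 − rho)) (change) and 0.5/sqrt(1 − rho²) (ANCOVA on baseline only). The 95% CI half-width for the post score is t(122) × 21 × sqrt(2/62) = 7.5 points. It is multiplied by sqrt(2(1 − rho)) for change and by sqrt(1 − rho²) for ANCOVA.

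| | rho 0.3 | rho 0.5 | rho 0.7 |
|---|---|---|---|
| Power, post score | 78.9% | 78.9% | 78.9% |
| Power, change score | 64.6% | 78.9% | 94.6% |
| Power, ANCOVA | 82.5% | 89.0% | 97.2% |
| Half-width, post score | 7.5 | 7.5 | 7.5 |
| Half-width, change score | 8.8 | 7.5 | 5.8 |
| Half-width, ANCOVA | 7.1 | 6.5 | 5.3 |

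**Effect of the strata.** A simulation used seven strata, blocks of 4 and 124 completers, with assumed stratum sizes 40/8/20/16/20/8/12, rho 0.3 to 0.8 and 16,000 runs per setting. The table shows type I error.

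| | Strata explain 0% | Strata explain 10% to 20% |
|---|---|---|
| Post score alone | about 5% | 2.5% to 4.2% |
| Change score alone | about 5% | 4.8% to 5.3% |
| Either | 8.8% to 9.6% | 6.7% to 8.6% |
| ANCOVA, baseline and strata | about 5% | 4.8% to 5.4% |

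Leaving out prognostic strata makes the post-score test conservative; it does not inflate alpha.

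**The case against.** The strongest reply is that the sample-size paragraph already implies the answer. General health is the only SF-36 scale the documents name. The calculation uses a control-group score and its SD, with no change-score SD and no correlation, which points to an unadjusted post-score comparison. On that reading the gap is one of labelling, and naming the post-score t test would close it as well as ANCOVA would. This test is valid and has 78.9% power, close to the planned 80%.

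The alpha figures are also conditional: nowhere does the plan say that success on either contrast is enough. The disagreement figures depend on an assumed rho and count p-values falling on different sides of 0.05. Significant results in opposite directions are practically absent (under 0.01% with no effect, for rho 0.3 to 0.7).

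Much of this stands. General health is the natural candidate, either-counts is a worst case, and the unadjusted tests are each valid. Two points survive. A sample-size assumption does not designate an endpoint, and the analysis text puts change scores on an equal footing with post-trial scores. Even if general health is accepted as primary, the choice of contrast stays open, and that alone produces the disagreement rates. ANCOVA does not settle the scale or the time point; these must be named as well. At rho 0.3 its gain is modest: 3.6 points of power and 0.4 points of half-width.

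**Conclusion.** The concern holds. The plan does not define its primary result: it fixes no scale and runs two between-arm contrasts without ranking them. At the planned effect and 62 per arm, the two give different verdicts at the 0.05 level in 21% to 27% of trials over rho 0.7 to 0.3. The 0.05 is exceeded only if significance on either could be claimed, and then by the amounts shown above. The sizes rest on assumed values of rho, stratum sizes and stratum R². The direction does not: two tests with either counting exceed the level of a single one unless strata make them conservative enough to offset it, which did not happen in the settings simulated.

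Naming one analysis is the part that must be fixed. Adjusting for baseline and stratum is a free improvement: in large samples ANCOVA is at least as precise as either unadjusted contrast whatever the value of rho.

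**What to change.** In Outcome Measures, name the SF-36 general health score at 6 months as the primary endpoint. In Data Analysis, name one primary analysis: a linear model for that score with treatment, baseline general health score and randomization stratum, pooling sparse strata to primary condition. Report the adjusted difference with its 95% CI at two-sided 0.05.

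Make change scores, the other SF-36 scales, the 1-month SF-36 and the rank-based tests secondary or sensitivity analyses. Label the within-arm paired tests as descriptive.

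The cost is a few sentences, to be written before outcome data are seen by arm. No patients, visits or data are added: the baseline and 6-month questionnaires and the strata are already collected, and the named software fits the model.

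### The between-arm tests leave out the strata used in randomization, so if condition predicts the SF-36 score they are conservative and forgo some power

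*Combined protocol and SAP*

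**What the plan says.** The randomization paragraph, under Patient Recruitment, states: "The participants will be blocked randomized (blocks of 4) and stratified into groups according to their primary condition". The five conditions follow: "stratified into groups according to their primary condition (HF, COPD, hypertension, insulin-requiring diabetes, and CKD". Two of them are split again. For heart failure: "The HF group will further be stratified based on NYHA classification (NYHA class 2-3, NYHA class 4". For hypertension: "the hypertensive patients will be stratified to those with and those without diabetes". That makes 2 + 1 + 2 + 1 + 1 = 7 lists.

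Under Outcome Measures: "The primary outcome will be health status as measured with SF-36". The sample size rests on one dimension of it: "Assuming a moderate effect size on the general health dimension of the SF-36 of 10.5 points".

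The Data Analysis paragraph is the whole quantitative plan for comparing arms: "Post-trial data and change scores will be compared between the control and intervention groups using independent Student t tests and Mann-Whitney tests". It adds paired tests within each arm and a cost evaluation. It names no stratum term, covariate, linear model or stratified rank test. The disease-specific sub-analyses mentioned under Outcome Measures concern cost and do not adjust the primary comparison.

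The number of lists is itself unsettled. The Abstract admits insulin-requiring diabetes only as a co-morbidity of one of the other four conditions, which would leave six lists. The Inclusion Criteria and the randomization paragraph treat it as a condition in its own right. These passages need to be reconciled; the argument here is the same with six lists or seven.

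**The concern.** Blocking within strata makes the arms nearly equal in their mix of conditions. Differences in health status between, say, heart failure and hypertension patients then contribute little to the real sampling error of the arm difference. A two-sample t test does not use this. It pools all patients within an arm and counts the between-condition spread as error. If that spread is real, the reported standard error exceeds the true one, the confidence interval is too wide, and the test rejects less often than 5% under the null. The Mann-Whitney test has the same fault in another form: its null variance is too large for the design.

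At stake is precision that the randomization has already provided. Stratum is recorded for every patient at randomization, so using it needs no new data.

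**Working it through.** **Inputs.** From the sample size paragraph under Patient Recruitment: difference 10.5 points, SD 21, two-sided alpha 0.05, power 80%, 63 per group, 15% loss, 73 per group, 146 in total. Assumed, because the documents give no figure: the share R² of outcome variance that lies between strata, taken as 0, 5, 10 and 20%.

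**The plan's own figure.** n per group = 2 × [21 × (1.960 + 0.842) / 10.5]² = 62.8, rounded up to 63, as stated. The 73 matches 63 × 1.15 = 72.45, rounded up. After 15% loss, 73 × 0.85 = 62.05, so about 62 per arm are evaluable.

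**Formulas (large-sample).**
- Standard error used by the t test: SE_u = 21 × √(2/62) = 3.77.
- True standard error under stratified blocking, which a stratum-adjusted model estimates: SE_a = 3.77 × √(1 − R²).
- True two-sided alpha of the unadjusted test: 2 × [1 − Φ(1.96 / √(1 − R²))].
- Unadjusted power: Φ[(10.5 − 1.96 × SE_u) / SE_a].
- Adjusted power: Φ(10.5 / SE_a − 1.96).

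Example at R² = 10%: SE_a = 3.77 × 0.949 = 3.58. Alpha = 2 × [1 − Φ(2.066)] = 3.9%. Unadjusted power = Φ(0.868) = 80.7%. Adjusted power = Φ(0.975) = 83.5%. The difference is 2.8 points.

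| R² (assumed) | SE used | True SE | True alpha, unadjusted | Power, unadjusted | Power, adjusted | Forgone (points) |
|---|---|---|---|---|---|---|
| 0% | 3.77 | 3.77 | 5.0% | 79.5% | 79.5% | 0 |
| 5% | 3.77 | 3.68 | 4.4% | 80.1% | 81.5% | 1.4 |
| 10% | 3.77 | 3.58 | 3.9% | 80.7% | 83.5% | 2.8 |
| 20% | 3.77 | 3.37 | 2.8% | 82.1% | 87.5% | 5.4 |

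From 5 to 20%, the standard error used is about 3 to 12% wider than the true one. The 79.5% in the first row, against 80.1% with 63 per arm, comes from having 62 evaluable patients and not from the strata.

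**Simulation check.** The set-up was 146 patients in seven lists with assumed shares of 30, 5, 15, 15, 15, 10 and 10%, blocks of 4, 15% random loss, and 10,000 runs per setting. For R² of 0, 5, 10 and 20%:
- Power, unadjusted against adjusted: 78.9 v 78.7%, 79.3 v 80.5%, 79.8 v 82.6% and 81.2 v 86.8%.
- Null rejection by the unadjusted test: 5.4, 4.8, 4.1 and 3.2%. By the adjusted model: 5.2, 5.2, 5.2 and 5.0%.

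The unadjusted test is slightly less conservative here than in the formula, because unfilled blocks and losses leave some imbalance within strata. The 0% setting shows the price of needless adjustment: about 0.2 points.

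**Overlap with baseline adjustment.** Baseline SF-36 is collected and carries much of any stable difference between conditions. Assume a within-stratum correlation of 0.5 to 0.7 between baseline and follow-up, and stratum means that stay constant over time. With 62 per arm, adding stratum to a model that already holds baseline then raises power by only about 0.1 to 0.5 points at R² = 10% and 0.1 to 0.8 points at 20%. Without stratum, that model's true alpha is already about 4.4 to 4.8%.

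**The case against.** The strongest reply is that nothing the plan promised is lost. The trial was sized for an unadjusted comparison with SD 21, and at R² of 5% or more that test has 80.1 to 82.1% power. A reader might infer from the mismatch that the trial is underpowered or its sample size wrong. The documents do not support that: power is lost only relative to a better analysis of the same data. Nor is there a false-positive risk, since the error is on the conservative side. This part of the reply stands.

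The size of the loss is also conditional. No document states how strongly primary condition, NYHA class or diabetes predicts SF-36, so it cannot be asserted that power is lost. At 0 to 5% the gain is at most 1.4 points. This stands too.

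The plan also tests change scores. Differencing removes any between-condition difference that is the same at baseline and at 6 months. If that were the only kind of difference, the strata would explain none of the variance in change, so the tabulated figures apply to post-trial scores.

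Finally, a reader might extend the point to every outcome, including cost and hospital use. The text does not carry it that far. Cost is described as setting savings against equipment and resource costs, not as a t test. COPD, CKD and diabetes measures, if analysed by primary condition, each fall within a single list and have no stratum variation to remove. No figure in the documents supports a larger effect for hospital use.

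The reply does not remove the mismatch itself: the design uses the strata, the between-arm tests do not, and using them costs almost nothing.

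**Conclusion.** The concern holds as a conditional loss of efficiency. The between-arm tests ignore strata that the randomization balances. If those strata predict post-trial SF-36 general health, the unstratified standard error is too wide and the test conservative. Over an assumed 0 to 20% of variance explained, true alpha runs from 5.0 down to about 2.8%, and the power forgone from 0 to about 5.4 points.

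These figures rest on SD 21, a 10.5-point difference, about 62 completers per arm, and an analysis of post-trial scores without baseline. They shrink for change scores and fall below 1 point once baseline SF-36 is in the model, under the correlations assumed above. They must therefore not be added to any gain claimed for baseline adjustment. The choice should be made before outcomes are seen, because a stratum term added later could look data-driven.

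**What to change.** In the Data Analysis paragraph:

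- Compare the arms on the primary SF-36 score and the other continuous patient outcomes with a linear model containing arm and randomization stratum, alongside the baseline value where it is collected. For heart failure measures the stratum is the NYHA split; for hypertension measures it is the diabetes split.
- Where a rank test is kept, use the van Elteren (stratified rank) test in place of Mann-Whitney.
- Fix in advance a rule for merging sparse strata. NYHA class 4 is the likely case; for example, a stratum with no evaluable patients in one arm is merged with its neighbour.
- Reconcile the Abstract with the Inclusion Criteria and the randomization paragraph on whether insulin-requiring diabetes can be a primary condition, so that the number of strata in the model is settled.

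The cost is a few sentences and a standard linear model in the planned software, with no new data and no more patients. The downside is up to six error degrees of freedom, which takes well under 1 point of power if the strata turn out not to be prognostic (78.9% against 78.7% in the simulation).
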